17. REGULATORY AND REPORTING REQUIREMENTS

This research will be done in compliance with the applicable State and Federal laws and regulations and in compliance with ICH guidelines. The study description will be posted on the www.clinicaltrials.gov website in compliance with current regulations. The data and safety plan will be executed in accordance with ICH

guidelines and in compliance with policy and procedures at the H. Lee Moffitt Cancer Center & Research Institute. The following must be observed to comply with Food and Drug Administration (FDA) regulations for the conduct and monitoring of clinical investigations; they also represent sound research practice:

1. Informed Consent

The investigator is responsible for patient care and for obtaining consent by the patient. Written informed consent must be obtained prior to entry of any patient. The original consent form signed and dated by the subject and by the person consenting the subject prior to the subject's entry into the study must be maintained in the Investigator's study files.

2. Use of Specimens For Research

The patient is free at any time in the future to decide not to provide specimens or to withdraw his/her specimens from further scientific research. Such a decision will have no impact on his/her treatment or other aspects of participation in this study.

3. Institutional Review

No subject is to be enrolled on this protocol until the Center's Institution Review Board has approved it. The protocol for this study has been designed in accordance with the general ethical principles outlined in the Declaration of Helsinki. The Investigator will be responsible for preparing documents for submission to the relevant IRB and obtaining written approval for this study. The approval will be obtained prior to the initiation of the study. The approval for both the protocol and informed consent must specify the date of approval, protocol number and version, or amendment number. Any amendments to the protocol after receipt of IRB approval must be submitted by the Investigator to the IRB for approval. The Investigator is also responsible for notifying the IRB of any serious deviations from the protocol, or anything else that may involve added risk to subjects.

4. Drug Accountability

For each drug supplied for a study, an accountability ledger containing current and accurate inventory records covering receipt, dispensing, and the return of study drug supplies must be maintained. Drug supplies must be kept in a secure, limited access storage area under the recommended storage conditions. These Accountability Forms must be readily available for inspection and are open to FDA inspection at any time.

5. IND Safety Reporting Requirements

This protocol is associated with an Investigational New Drug Application (IND) supported by Aprea. IND Safety Reports are required for any adverse experience associated (or possibly associated) with the use of investigational product(s) that is both serious and unexpected. To meet the IND Safety reporting requirements set forth in 21 CFR§312.32, an FDA Form 3500A (MedWatch form) will be completed and provided to the Moffitt Office of Institutional Regulatory Affairs for Investigational Drugs and Devices. All other adverse events will be reported to the FDA as part of the annual reporting requirement of the IND.

The initial report will include details of the current illness and serious adverse events, and an assessment of the causal relationship between the event and the investigational product(s). Information not available at the time of the initial report (e.g., an end date for the adverse event or laboratory values received after the report) will be documented on the follow-up report. A final report to document resolution of the serious adverse event is required if it is not documented in the initial report. The Moffitt Office of Institutional Regulatory Affairs will provide the report to the FDA as an official submission to the IND. This will occur independently of any other use of the MedWatch form or required reporting of serious adverse events. Submission of the MedWatch form to any other agency, including the FDA, does not fulfill this IND Safety Reporting requirement. Follow-up to the safety report must also be submitted to the Office of Institutional Regulatory Affairs in a timely manner. Upon completion of the report, a copy of all initial and follow-up MedWatch forms will be scanned and emailed to the Office of Institutional Regulatory Affairs and a telephone call will be made to confirm receipt. For unexpected fatal or life threatening experiences associated with the use of the investigational product(s), the Office of Institutional Regulatory Affairs will be contacted upon notice of the event. Notification to the FDA will be made as soon as possible, but no later than 7 calendar days after initial receipt of the information.

6. Hospital/Clinic Records

Hospital records for patients on this study are the responsibility of the investigator. They will be available for review by the sponsors of the trial, health care personnel involved in this study, the IRB, DHHS, and the FDA.

7. Investigator Study Files

The Principal Investigator is responsible for maintaining study files for a period of 2 years following the date a marketing application is approved for the drug for the indication for which it is being investigated; or if no

application is to be filed or if the application is not approved for such indication, until 2 years after the investigation is discontinued and FDA is notified.

The following documents should be kept in the study files:

- A completed, signed FDA Form 1572 (Statement of Investigator) and copies of all current curricula vitae of all sub investigators listed on the Statement of the Investigator.
- The original protocol and all amendments
- Final IRB approval, annual renewals and all IRB correspondence
- Blank Case Report Forms
- Copy of all IRB approved Informed Consent forms with applicable version date
- Updated laboratory certification and laboratory values (covering entire time of study)
- Copy of all patient's signed informed consent forms
- The final completed case report form for all patients

8. STUDY MONITORING

The Protocol Review & Monitoring Committee will monitor this study. Regulatory documents and case report forms will be reviewed routinely by the MCC Clinical Research Monitoring Core for accuracy, completeness and source verification of data entry, validation of appropriate informed consent process, adherence to study procedures, and reporting of SAEs and protocol deviations according to MCC Monitoring Policies. As part of the responsibilities assumed by participating in the study, the Investigator agrees to maintain and have available for monitoring adequate case records (accurate source documents and CRFs) for the subjects treated under this protocol. CRFs will only be required for patients who have received at least one dose of study medication. In addition, the Investigator agrees to maintain all administrative documents, e.g., IRB/IEC correspondence, investigational product and supplies shipment manifests, monitoring logs, or Moffitt Cancer Center/designee correspondence. The PI will be primarily responsible for monitoring of adverse events, protocol violations, and other immediate protocol issues. The study coordinator will collect information of subjects enrolled at Moffitt and other institutions through the use of electronic or paper AE forms, CRF forms, End of Study forms, and Informed Consent forms.

Internal Monitoring

Data will be captured in Oncore, Moffitt's Clinical Trials Database. The Case Report Forms will be reviewed by Moffitt's Internal Monitors, periodically, throughout the conduct of the trial. The monitoring will include source data verification, utilizing research subjects' medical records.

On-site Audits

The Investigator should promptly notify Moffitt Cancer Center or its authorized representative of any audits scheduled by any regulatory authorities and promptly forward copies of any audit reports received to Moffitt Cancer Center or its authorized representative.

Data & Safety Monitoring Plan

Identification of oversight responsibility:

The PI has primary responsibility.

The MCC Protocol Monitoring Committee (PMC):

The PMC meets monthly and reviews accrual, patterns and frequencies of all adverse events, protocol violations and when applicable, internal audit results.

Description of internal (PI) safety review and monitoring process:

Responsible for identifying and reviewing adverse events biweekly:

Principal Investigator

Study team

To be reviewed:

Adverse events by grade (Gr. 3 or above using CTCAE v4.03) and attribution (expected or unexpected)

Relationship to study drug/intervention

Application of dose finding escalation/de-escalation rules

Application of study designed stopping/decision rules

Whether the study accrual pattern warrants continuation/action

Protocol violations

AEs will be reported along with all other data in the Oncore database. The PI or PI designate will report all adverse events to the Clinical Research Office (CRO). The CRO will report all SAEs to Aprea, and all reportable SAEs to the IRB. AE information will be entered into the CRO database. AE information will be managed by the CRO and will be made available to the PMC or appropriate monitoring body by designated members of the PMC or the study statisticians.

APPENDIX A

Performance Status Criteria

ECOG Performance Status Scale		Karnofsky Performance Scale	
Grade	Descriptions	Percent	Description
0	Normal activity. Fully active, able to carry on all pre-disease performance without restriction.	100	Normal, no complaints, no evidence of disease.
		90	Able to carry on normal activity; minor signs or symptoms of disease.
1	Symptoms, but ambulatory. Restricted in physically strenuous activity, but ambulatory and able to carry out work of a light or sedentary nature (e.g., light housework, office work).	80	Normal activity with effort; some signs or symptoms of disease.
		70	Cares for self, unable to carry on normal activity or to do active work.
2	In bed <50% of the time. Ambulatory and capable of all self-care, but unable to carry out any work activities. Up and about more than 50% of waking hours.	60	Requires occasional assistance, but is able to care for most of his/her needs.
		50	Requires considerable assistance and frequent medical care.
3	In bed >50% of the time. Capable of only limited self-care, confined to bed or chair more than 50% of waking hours.	40	Disabled, requires special care and assistance.
		30	Severely disabled, hospitalization indicated. Death not imminent.
4	100% bedridden. Completely disabled. Cannot carry on any self-care. Totally confined to bed or chair.	20	Very sick, hospitalization indicated. Death not imminent.
		10	Moribund, fatal processes progressing rapidly.
5	Dead.	0	Dead.

APPENDIX B

RESPONSE CRITERIA FOR SUBJECTS WITH MDS AND CMML ACCORDING IWG 2006 CRITERIA³⁴

ALTERING DISEASE NATURAL HISTORY	
Complete remission (CR)	Bone marrow: $\leq 5\%$ myeloblasts with normal maturation of all cell lines Persistent dysplasia will be noted Peripheral blood: Hemoglobin ≥ 11 g/dL Platelets $\geq 100 \times 10^9/L$ Neutrophils $\geq 1.0 \times 10^9/L$ Blasts 0%
Partial remission (PR)	All CR criteria if abnormal before treatment, except: Bone marrow blasts decreased by $\geq 50\%$ over pretreatment but still $> 5\%$ Cellularity and morphology not relevant
Marrow CR	Bone marrow: $\leq 5\%$ myeloblasts and decrease by $\geq 50\%$ over pretreatment Peripheral blood: if HI responses, they will be noted in addition to marrow CR
Stable disease (SD)	Failure to achieve at least PR, but no evidence of progression for > 8 weeks
Failure	Death during treatment Disease progression characterized by worsening of cytopenias, increase in % of bone marrow blasts, or progression to a more advanced MDS FAB subtype than pretreatment
Disease Progression (PD)	For subjects with: Less than 5% blasts: $\geq 50\%$ increase in blasts to $> 5\%$ blasts 5%-10% blasts: $\geq 50\%$ increase in blasts to $> 10\%$ blasts 10%-20% blasts: $\geq 50\%$ increase in blasts to $> 20\%$ blasts 20%-30% blasts: $\geq 50\%$ increase in blasts to $> 30\%$ blasts Any of the following: At least 50% decrement from maximum remission/response levels in granulocytes or platelets Reduction in hemoglobin (Hgb) concentration by ≥ 2 g/dL - Transfusion dependence
CYTOGENETIC RESPONSE	
Complete	Disappearance of the chromosomal abnormality without appearance of new ones
Partial	At least 50% reduction of the chromosomal abnormality
HEMATOLOGICAL IMPROVEMENT (HI)	
Erythroid response (HI-E) (Pretreatment < 11 g/dL)	Hgb increase by ≥ 1.5 g/dL Relevant reduction of units of RBC transfusions by an absolute number of at least 4 RBC transfusions/8 weeks compared with the pretreatment transfusion number in the previous 8 weeks. Only RBC transfusions given for a Hgb of ≤ 9.0 g/dL pretreatment will count in the RBC transfusion evaluation
Platelet response (HI-P) (Pretreatment $< 100 \times 10^9/L$)	Absolute increase of $\geq 30 \times 10^9/L$ for subjects starting with $> 20 \times 10^9/L$ Increase from $< 20 \times 10^9/L$ to $> 20 \times 10^9/L$ and by at least 100%
Neutrophil response (HI-N) (Pretreatment $< 1.0 \times 10^9/L$)	At least 100% increase and an absolute increase of $> 0.5 \times 10^9/L$

PROGRESSION/RELAPSE CRITERIA FOR SUBJECTS WITH MDS/CMML

ALTERING DISEASE NATURAL HISTORY	
Disease Progression (PD)	
For subjects with:
 
Less than 5% blasts: $\geq 50\%$ increase in blasts to $> 5\%$ blasts
 
5%-10% blasts: $\geq 50\%$ increase in blasts to $> 10\%$ blasts
 
10%-20% blasts: $\geq 50\%$ increase in blasts to $> 20\%$ blasts
 
20%-30% blasts: $\geq 50\%$ increase in blasts to $> 30\%$ blasts
 
Any of the following:
 
At least 50% decrement from maximum remission/response levels in granulocytes or platelets
 
Reduction in hemoglobin (Hgb) concentration by ≥ 2 g/dL
 
Transfusion dependence

Disease transformation	Transformation to AML (30% or more blasts)
Relapse after CR or PR	
At least one of the following:
 
Return to pretreatment bone marrow blast %
 
Decrement of $\geq 50\%$ from maximum remission/response levels in granulocytes or platelets
 
- Reduction in Hgb concentration by ≥ 1.5 g/dL or transfusion dependence

HEMATOLOGICAL IMPROVEMENT	
Progression/relapse after HI	
At least one of the following:
 
At least 50% decrement from maximum response levels in granulocytes or platelets
 
Reduction in Hgb by ≥ 1.5 g/dL
 
- Transfusion dependence

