4. PATIENT SELECTION

4.1. Eligibility criteria

Inclusion Criteria:

1. Patient has signed the Informed Consent (ICF) and is able to comply with protocol requirements
2. Patient has adequate organ function as defined by the following laboratory values:
 - a. Serum creatinine ≤ 2 x upper limit of normal (ULN)
 - b. Total serum bilirubin < 1.5 x ULN or total bilirubin ≤ 3.0 x ULN with direct bilirubin within normal range in patients with well documented Gilbert's Syndrome or

hemolysis or who required regular blood transfusions

- c. Alanine aminotransferase (ALT) and aspartate aminotransferase (AST) $< 2.5 \times \text{ULN}$
3. Age ≥ 18 years at the time of signing the informed consent form
4. Documented diagnosis of myelodysplastic syndrome (MDS), MDS/ myeloproliferative neoplasm (MPN), chronic myelomonocytic leukemia (CMML) by WHO criteria or AML with 20-30% myeloblasts (refractory anemia with excess blasts in transformation (RAEB-T) by French-American-British (FAB) criteria)
5. Documentation of a *TP53* gene mutation by NGS based on central or local evaluation
6. Revised International Prognostic Scoring System (IPSS-R) criteria for Intermediate, High-risk or Very High-risk.
7. An Eastern Cooperative Oncology Group (ECOG) performance status score of 0, 1, or 2 is required.
8. If of childbearing potential, negative pre-treatment urine or serum pregnancy test.
9. If of childbearing potential (males and females), willing to use an effective form of contraception such as latex condom, hormonal birth control, intrauterine device or double barrier method during chemotherapy treatment and for at least six months thereafter.

Exclusion Criteria

1. Patient has a known history of HIV or active hepatitis B or active hepatitis C infection (testing not mandatory).
2. Patient has any of the following cardiac abnormalities (as determined by treating MD):
 - a. Symptomatic congestive heart failure
 - b. Myocardial infarction ≤ 6 months prior to enrollment
 - c. Unstable angina pectoris
 - d. Serious uncontrolled cardiac arrhythmia
 - e. QTc ≥ 470 msec
3. Concomitant malignancies or previous malignancies with less than a 1-year disease free interval at the time of signing consent. Patients with adequately resected basal or squamous cell carcinoma of the skin, or adequately resected carcinoma in situ (e.g. cervix) may enroll irrespective of the time of diagnosis.
4. Prior exposure to azacitidine, decitabine or investigational hypomethylating agent.

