Patients requiring a dose delay of > 28 days must be permanently discontinued from study drug. Following 4 cycles of therapy for responding patients (i.e. CR, PR, HI, or marrow CR), treatment with APR-246 and azacitidine can be delayed per the study investigator for up to 14 days to allow for count recovery or at investigator discretion post discussion with Moffitt PI. Non-hematologic grade 4 treatment related adverse events will lead to permanent discontinuation, irrespective of recovery time, unless otherwise specified. Exceptions would include nausea/vomiting/diarrhea which can be controlled by medications and/or asymptomatic electrolyte imbalances which can be corrected. In addition, in most instances, patients that experience a prolonged treatment interruption because of an adverse event and/or a grade 3 adverse event will decrease the dose of study drug after their recovery (see specific tables for dose adjustment guidelines). Furthermore, patients requiring >1 dose reduction for APR-246 will be permanently discontinued from study drug. Patients who permanently discontinue all study drugs should have follow-up within 30 days after discontinuation of all study treatment or resolution of the AE to \leq grade 1, whichever occurs first, that includes all study assessments appropriate to monitor the event.

4. DLT Definition

Patients will be evaluated for DLTs during the lead-in phase and first cycle of combination therapy, i.e., 6 weeks for purpose of deciding the dose for next cohort (see Table 1) but DLTs will continue to be evaluated and reported through all cycles on study. DLT is defined as follows based on the CTCAE v 4.03:

- Treatment related non-hematological CTCAE grade 3-4 toxicity that lead to dose modification or withdrawal.
- Absolute neutrophil count (ANC) not recovering to $>500/\mu\text{L}$ by day 42 of a cycle in the absence of active leukemia/myelodysplasia will be considered a DLT.
- Grade 3 metabolic/electrolyte abnormalities that are not clinically significant, and are adequately controlled within 72 hours are not to be considered DLT.
- Grade 3 nausea/vomiting/diarrhea or CNS toxicity that does not resolve within 28 days despite treatment interruption and maximum medical therapy will be considered a DLT.

5. Criteria for APR-246 dose modifications (Phase 2)

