- i. Duration of response defined as the time between achieving response and progression of disease.
- ii. OS at 8 months
- iii. Proportion of subjects achieving hematological improvement (HI), partial response (PR), complete response (CR), and/or marrow CR (mCR) by the IWG 2006 criteria (see appendix B)
- iv. Proportion of subjects who obtain a response as defined by IWG 2006 criteria with a baseline *TP53* VAF $\geq 20\%$ versus $< 20\%$ or high versus low nuclear p53 protein expression

- v. Correlation of *TP53* VAF with nuclear p53 protein expression as determined by IHC
- vi. Proportion of subjects who achieve $\geq 50\%$ reduction in *TP53* VAF.
- vii. Progression free survival (PFS) and OS in clonal responders ($\geq 50\%$ reduction in *TP53* VAF) versus non-responders
- viii. Profile expression of genes related to p53-mediated signal transduction before and after APR-246 treatment
- ix. Profile ROS production before and after APR-246 treatment
- x. AML transformation according to World Health Organization (WHO) criteria
- xi. OS
- xii. LFS
- xiii. Determine recurrent gene mutations in *ASXL1*, *BCOR*, *BRAF*, *CALR*, *CBL*, *CEBPA*, *CSF3R*, *DNMT3A*, *ETV6*, *EZH2*, *GATA2*, *GNAS*, *IDH1*, *IDH2*, *JAK2*, *KIT*, *KRAS*, *MPL*, *NF1*, *NPM1*, *NRAS*, *PDGFRA*, *PDGFRB*, *PHF6*, *PTPN11*, *RAD21*, *RUNX1*, *SETBP1*, *SF3B1*, *SMC1A*, *SMC3*, *SRSF2*, *STAG2*, *STAT3*, *STAT5b*, *TET2*, *TP53*, *U2AF1*, *WT1*, and *ZRSR2* at study entry and serially throughout treatment to assess changes in somatic mutation landscape.

Preliminary data on the above endpoints will prove to be very useful for further investigation of this protocol's treatment. Such data will be summarized appropriately in an exploratory fashion. Both point estimates and 95% confidence intervals will be reported, if feasible. Time-to-event endpoints such as OS and LFS will be summarized using the Kaplan-Meier product-limit method.

16. Laboratory Correlates

Unless otherwise specified, all laboratory correlates will be performed in the laboratory of [name] or at Genoptix medical laboratory.

1. Mutation analyses

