APPENDIX C: 2016 WHO CLASSIFICATION FOR CMML AND MDS³⁵
WHO CMML

WHO Subtype	Peripheral Blood	Bone Marrow
#Chronic Myelomonocytic Leukemia *CMML-0 **CMML-1 ***CMML-2	*<2% blasts **≥2% and <5% blasts ***≥5% and <20% blasts persistent monocytosis > 1 x 10 ⁹ /L and >10% of differential +/- cytopenias Leukocytosis frequent	* <5% blasts **≥5% and <10% blasts ***<20% blasts >10% dysplasia in affected lineage ***Auer Rods The absence of the Philadelphia chromosome of bcr-abl fusion gene.

[#]Not meeting WHO criteria for *BCR-ABL1* CML, PMF, PV, or ET. No evidence of *PDGFRA*, *PDGFRB*, or *FGFR1* rearrangement or *PCMI-JAK2* (should be specifically excluded in cases with eosinophilia). If myelodysplasia is absent or minimal, CMML diagnosis can be made with acquired clonal cytogenetic/molecular genetic abnormality or monocytosis x 3 months when all other causes of monocytosis have been excluded. Blasts and blast equivalents include myeloblasts, monoblasts, and promonocytes.

WHO MDS

WHO Category	Peripheral blood	Bone marrow
MDS with single lineage dysplasia (MDS-SLD)	Cytopenia (1-2 lines) <1% blasts	Dysplasia (1 line) < 5% blasts RS <15%/<5%†
MDS with ring sideroblasts (MDS-RS)*	Cytopenia (1-3 lines) < 1% blasts	Dysplasia (1-3 lines) < 5% blasts RS >15%/>5%†
MDS with multi-lineage dysplasia (MDS-MLD)	Cytopenia (1-3 lines) < 1%blasts	Dysplasia (2-3 lines) < 5% blasts RS <15%/<5%†
MDS with excess blasts type I & II (MDS-EB-1 & MDS-EB-2**)	Cytopenia (0-3 lines) Type I: 2-4% blasts Type II: 5-19% blasts	Dysplasia (1-3 lines) Type I 5-9% blasts Type II 10-19% blasts
MDS with isolated del(5q)***	Cytopenia (1-2 lines) < 1% blasts	Dysplasia (1-3 lines) < 5% blasts
MDS unclassified (MDS-U)****	Cytopenia (0-3 lines) 1% or < 1% blasts	Dysplasia (1-3 lines) < 5% blasts

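### Marrow CR in Appendix B has no pretreatment blast minimum, so patients who enter at 5% blasts or fewer can be scored as responders in the overall response rate, partly through count error

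*Combined protocol and SAP*

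**What the plan says.** Appendix B defines marrow CR by two conditions: follow-up marrow blasts no higher than 5%, and "myeloblasts and decrease by $\geq 50\%$ over pretreatment". It states no minimum pretreatment level, no minimum absolute fall and no confirmatory marrow. Section 14 refers back to Appendix B and adds nothing.

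Low-blast patients can enrol. Section 4.1 asks for "Documented diagnosis of myelodysplastic syndrome (MDS), MDS/ myeloproliferative neoplasm (MPN), chronic myelomonocytic leukemia (CMML) by WHO criteria" (or AML with 20-30% blasts) and for "Revised International Prognostic Scoring System (IPSS-R) criteria for Intermediate, High-risk or Very High-risk", with no blast floor for MDS or CMML. Appendix C lists several qualifying categories with low marrow blasts, for example MDS with multilineage dysplasia: "Dysplasia (2-3 lines) < 5% blasts". The progression row of Appendix B has a stratum for them: "Less than 5% blasts: $\geq 50\%$ increase in blasts to $> 5\%$ blasts".

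Marrow CR is named in secondary endpoint iii of Section 15.4: "Proportion of subjects achieving hematological improvement (HI), partial response (PR), complete response (CR), and/or marrow CR (mCR". Endpoint i (duration of response) and endpoint iv (response by TP53 VAF or p53 expression) speak of response without listing its components. The nearest thing to a definition is in the dose-delay text of Section 10, which speaks of "responding patients (i.e. CR, PR, HI, or marrow CR".

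**The concern.** A patient with 2% blasts at entry already meets the blast level that marrow CR is meant to certify. Under the printed rule, a later reading of 1% makes that patient a responder. At these levels a halving can be a difference of a few cells, so some such responses would come from the count and not from treatment.

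The neighbouring rows of Appendix B have a guard that this one lacks. Each HI row carries a pretreatment threshold, PR requires blasts still above 5%, and progression from below 5% requires a rise past 5%.

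At stake is an overall response rate, in a single-arm trial, that includes patients scored on noise. If marrow CR also starts the clock for duration of response, there is a second asymmetry. A fall from 2% to 1% would open a response, but a return to 2% would not close it on blasts, and Appendix B gives relapse criteria after CR or PR and after HI but none after marrow CR. In the VAF/p53 comparison, false responders would blur any real difference.

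**Working it through.** **The plan's own figures.** The documents give none for marrow CR or for count error. The only design figures concern the primary endpoint, CR. For the rule 5/24 then 13/45, exact binomial calculation gives early termination 0.656 at a 20% CR rate (stated 0.66), alpha 0.0483 (stated 0.05) and power 0.9001 at 40% (stated 90%). They reproduce and do not involve marrow CR.

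**Does the rule admit low-blast patients?** Yes. 4% to 2%, 3% to 1.5% and 2% to 1% are each a 50% fall ending at or below 5%.

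**How often would count error alone produce it?**

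Inputs from the documents:
- the two Appendix B conditions;
- scheduled marrows after cycles 3 and 6 (Section 13).

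Assumptions:
- the true blast fraction p does not change, and is 1%, 2%, 3% or 4%;
- m = 200 or 500 cells are counted;
- error is binomial only. Sampling-site and reader variation are left out and would add to it.

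Let the baseline count X1 and each follow-up count X2 be independent Binomial(m, p), with probability f and cumulative probability F. Condition on an observed baseline of 5% or less, that is X1 ≤ 0.05m. For one marrow:

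P = [sum over a = 1 to 0.05m of f(a) × F(floor(a/2))] / P(X1 ≤ 0.05m)

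For either of two marrows, replace F by 1 − (1 − F)². Both follow-ups share one baseline, so the two-marrow figure is not the square rule applied to the one-marrow figure.

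Example, m = 200 and p = 2%: the numerator is 0.2163, and 0.2163 / 0.997 = 0.217. For p = 4%: 0.0567 / 0.82 = 0.069.

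| True blasts | 200 cells: one / two marrows | 500 cells: one / two marrows |
|---|---|---|
| 1% | 31.9% / 48.9% | 18.3% / 31.1% |
| 2% | 21.7% / 36.1% | 8.2% / 14.9% |
| 3% | 13.6% / 24.2% | 3.8% / 7.1% |
| 4% | 6.9% / 13.0% | 1.0% / 2.1% |

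**Effect on endpoint iii.** Added response rate = share entering at 5% or less × two-marrow probability. The share is not in the documents; 10% to 30% is assumed.
- Low end: 0.10 × 0.021 = 0.0021, about 0.2 points, or 45 × 0.0021 = 0.1 patients of 45.
- Intermediate (true 2%, 500 cells, share 20%): 0.20 × 0.149 = 0.030, about 3 points.
- High end: 0.30 × 0.489 = 0.147, about 15 points, or 45 × 0.147 = 6.6 patients of 45.

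Each figure is a ceiling under its own assumptions, because some of these patients would also reach CR or HI and count as responders anyway.

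**What a pretreatment requirement above 5% leaves behind.** False marrow CR becomes impossible for an observed baseline of 5% or less. A patient whose true level is below 5% but who reads above it can still be scored. Joint probabilities at one marrow with 200 cells, baseline read at or below 5% versus above 5%:
- true 2%: 21.6% versus 0.2%;
- true 3%: 13.1% versus 2.1%;
- true 4%: 5.7% versus 5.2%.

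The restriction removes nearly all the noise at 2% and about half at 4%.

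**The case against.** **The endpoints are minor.** The plan calls the secondary analyses exploratory. CR, the Simon rules, OS, LFS and the analyses defined by VAF reduction do not use marrow CR. This stands and limits the weight of the point. A reader might infer that the go/no-go decision is compromised; it is not.

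**The size is soft.** This also stands. Neither the cell count nor the low-blast share is documented. The top of the range needs a 200-cell count, every low-blast patient at a true 1%, a 30% share, and both marrows done in each. A reader might take a fall from 4% to 2% as the typical noise response. It is the least noise-prone case tabulated: 1.0% per marrow at 500 cells and 6.9% at 200.

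**Endpoints i and iv may not include marrow CR.** Fair. The wording that suggests they do is a dose-delay provision and not an endpoint definition, and Appendix B defines stable disease as falling short of at least PR. A reader might infer that duration of response and the biomarker comparison are certainly affected. The text supports that only conditionally.

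**The row is part of a cited standard.** Section 14 describes the criteria as modified IWG 2006. Whether the cited source carries a baseline condition cannot be checked from the documents. A restriction would depart from Appendix B as printed, which is a reason to report both versions.

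**HI denominators.** A reader might extend the argument to HI, since patients above a lineage threshold cannot score that HI. No lineage-specific HI rate is planned. Endpoint iii is one composite over all treated subjects, so nothing in the documents is distorted in that way.

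**Conclusion.** The concern holds for endpoint iii. As printed, marrow CR can be awarded to a patient who was already at the remission blast level at entry, such patients are eligible, and no other section closes the gap. For endpoints i and iv it holds only if response there includes marrow CR, which the plan should settle.

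The chance of a false marrow CR over two marrows lies between 2.1% and 48.9% per low-blast patient, for true blasts of 1% to 4% and 200 or 500 cells. With an assumed 10% to 30% of patients entering at 5% or less, that adds about 0.2 to 15 points to the response rate before overlap with CR and HI is removed. The existence of the gap rests on the documents; its size rests on assumptions. It is worth correcting because the correction is cheap, but it does not touch the primary conclusion.

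**What to change.** In Section 15.4:

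- For endpoint iii, count marrow CR only in patients whose pretreatment marrow blasts exceed 5%, which is Appendix B's own remission level.
- Keep all treated subjects as the denominator of the composite, and also give the marrow CR rate among patients who entered above 5%.
- Report the composite under the printed Appendix B rule alongside, so that the result stays comparable with the criteria as cited.
- State whether response in endpoints i and iv includes marrow CR. If it does, apply the same restriction there.

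This concerns endpoint scoring only; the dose-delay text of Section 10 is not part of the change. It uses blast counts already collected and leaves the sample size, the CR analysis and the Simon rules as they are. The cost is a slightly lower headline response rate and one extra table line. Some count noise remains for patients near the 5% cut-off.
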